### **Prior or Current Medications**

21. Received any investigational drug within 30-days prior to screening visit.
22. Received a live vaccine product within 14 days of study drug administration (Day 1) or expect to receive live vaccine during the Treatment Period (receiving a live vaccine within 14 days prior to enrollment is allowed).
23. Treatment with a hypoxia-inducible factor (HIF) stabilizer (e.g., molidustat, roxadustat) or an erythropoietin-mimetic, e.g., erythropoietin alpha or beta, darbopoietin alpha, or continuous erythropoiesis receptor activator (CERA), within 6-weeks prior to randomization or during treatment period.
24. Expected to receive any investigational drug or any of the exclusionary drugs listed in Section 15.1 during the Treatment Period or Safety Follow-Up Period.
25. Chronic use of systemic immunosuppressive drugs during the screening period or anticipated use of such drugs any time during the study. Note: Use of otic, ophthalmic, inhaled, and topical corticosteroids or local corticosteroid injections are not exclusionary. Oral prednisone up to 5 mg per day is (or equivalent) is permitted if dose has been stable for at least 4 weeks prior to screening, and no dose changes are planned during study participation.
26. Use of systemic antibiotics, systemic antivirals, or systemic antifungals during the screening period (“Systemic” is defined as oral or intravenous drugs that are absorbed into the circulation).
27. Requiring an indwelling catheter of any type.

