### **3.7 Benefit and Risk Assessment**

Despite the fact that the concept of inflammatory risk in renal patients has been in the public domain for decades, with an active basic research and clinical investigational community focused on its remediation, no therapy has been specifically designed or developed to address it. The advancement of an anti-inflammatory therapy for CKD patients should offer the benefit of myocardial protection and potential treatment of heart failure in this otherwise vulnerable population.

As for the risks associated with administration of Ziltivekimab, nonclinical toxicology studies established the NOAEL by the maximal dose administered (see the Ziltivekimab IB). Both in terms of local and systemic effects, Ziltivekimab was well tolerated, with no apparent adverse findings. Of note, the highest Ziltivekimab dose planned for study allows an over 20-fold margin to NOAEL in the non-clinical toxicology program.

Available data for anti-IL6R (tocilizumab) and anti-IL6 (siltuximab) therapies suggest neutralization of IL-6 have acceptable safety and tolerability profiles for the indications studied. Injection-related and life-threatening hypersensitivity reactions are rare with these agents. Anti-inflammatory therapies in general run the risk of inducing immune suppression and promoting the emergence of infections, sometimes serious in nature. Although anti-IL-6 therapies lower neutrophil counts and may induce frank neutropenia, their rates of infectious complications appear to be similar to other immune-modulatory biologic agents when accounting for patient-specific factors ([Sakai 2015](#), [Sanofi 2016](#)). Gastrointestinal perforation has been associated with anti-IL-6 therapy, however data suggests proper exclusion criteria may mitigate these risks ([Tanaka 2014](#)).

On balance then, the Sponsor proposes the potential risks to patients in this study are justifiable and the benefit-to-risk ratio positive. Patients will be consented as to the potential risks and will be required to sign an ICF documenting their understanding of these risks and willingness to participate in the study.

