## 4 SELECTION OF STUDY POPULATION AND CRITERIA FOR WITHDRAWAL

### 4.1 Inclusion Criteria

After signing an informed consent form approved by the Investigator's Institutional Review Board (IRB) or Independent Ethics Committee (IEC) to be eligible, potential study patients must meet all of the following criteria:

- 1) Age  $\geq 18$  years at the time of signing of the Informed Consent Form (ICF).
- 2) Stage 3-5 NDD-CKD, i.e. estimated glomerular filtration rate (eGFR)  $>10$  and  $<60$  mL/min/1.73 m^2 using the CKD-EPI Creatinine Equation ([www.kidney.org/content/ckd-epi-creatinine-equation-2009](http://www.kidney.org/content/ckd-epi-creatinine-equation-2009)).
- 3) Serum hs-CRP level  $\geq 2.0$  mg/L measured during the Screening Period. (Note: C-reactive protein may not be commonly measured in patients with CKD. Targeting patients with a history of advanced stage CKD, ASCVD, anemia, metabolic syndrome, diabetic retinopathy and diabetes for screening will help increase the chances of identifying patients with CRP  $\geq 2.0$ )
- 4) The patient agrees to comply with the contraception and reproduction restrictions of the study ([Appendix G](#)):
  - a) Women of childbearing potential must be using a method of contraception, that is "highly effective" (i.e.,  $<1\%$  failure rate) for at least 3 months following the last dose of study drug;
  - b) Postmenopausal women must have had no menstrual bleeding for at least 1 year before initial dosing and either be over the age of 60-years or have an elevated plasma follicle-stimulating hormone (FSH) level (i.e.,  $>40$  mIU/mL) at Screening;
  - c) Women of childbearing potential must have a documented negative pregnancy test result at Screening. Patients with elevated  $\beta$ -HCG levels believed to be due to end-stage renal disease may be enrolled if documented to not be pregnant;

AND

All male patients, from the day of dosing until the final study visit, unless surgically sterile, must be willing to use a condom with a partner (male patients with partners of childbearing potential must be willing to use 2 effective methods of birth control, 1 should be condom with spermicide) to prevent pregnancy and drug exposure of a partner, and refrain from donating sperm or fathering a child.

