### **5.1                   Screening Visit Procedures (Up to 2 weeks, Days -14 to -7) – Initial Screening**

Screening will be conducted in a stepwise manner. If a Screening laboratory result is outside inclusion criteria parameters screening may be extended up to one week to allow for retesting of lab test(s) that did not meet inclusion criteria.

Prior to conducting any study procedures informed consent will be obtained from the patient by the investigator (or other study staff who are conducting the informed consent interview). The Initial Screening procedures will be conducted after informed consent has been obtained. The following will be performed according to [Table 2](#).

- ICF signed
- Hematology
- Chemistry
- Iron Indices
- TMPRSS6 Genotype
- hs-CRP (may be repeated once up to randomization)
- Screening IL-6 (total)

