#### **5.3.1 Visit 1, Week 1, Day 1 (Pre-Dose)**

- Medical History (update if necessary)
- Randomization (may occur on Day -1 if needed)
- Concomitant and Prior Medications
- Vital Signs
- BMI
- Hematology
- Lipids (fasting 8 hours)

- Chemistry
- Urinalysis (including albumin); portion stored frozen
- Iron indices
- Serum hepcidin
- Special RBCs
- IL-6 (pre-dose)
- hs-CRP
- Ziltivekimab trough PK
- ADA (pre-dose)
- CKD Biomarkers
- NT-pro-BNP
- Lp(a), ApoB, ApoA1 (fasting 8 hours)
- Lipid profile by NMR spectroscopy (fasting 8 hours)
- Cardiac Biomarkers: SSA, fibrinogen and ST2
- Coagulation (INR): Patients on warfarin only
- Adverse Events
- PROMIS® 13a and Fatigue Items
- PROMIS® Sexual Interest Items
- Optum SF-36 v2® Health Survey
- EQ-5D-5L

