## 9.2 Serious Adverse Event Definition

An SAE is any AE, occurring at any dose and regardless of causality, that:

- Results in death;
- Is life-threatening. Life-threatening means that in the opinion of the Investigator or Study Sponsor, the patient was at immediate risk of death from the reaction as it occurred, (i.e., it does not include a reaction that hypothetically might have caused death had it occurred in a more severe form);
- Requires inpatient hospitalization or prolongation of existing hospitalization. Hospitalization admissions and/or surgical operations scheduled to occur during the study period, but planned before the signing for the ICF, are not considered AEs if the illness or disease existed before the patient was enrolled in the trial, provided that it did not deteriorate in an unexpected manner during the trial (e.g., surgery performed earlier than planned);
- Results in persistent or significant disability/incapacity. Disability is defined as a substantial disruption of a person's ability to conduct normal life functions;
- Is a congenital anomaly/birth defect;
- Is an important medical event. An important medical event is an event that may not result in death, be life-threatening, or require hospitalization but may be considered an SAE when, based upon appropriate medical judgment, it may jeopardize the patient and may require medical or surgical intervention to prevent one of the outcomes listed in the definitions for SAEs. Examples of such medical events include allergic bronchospasm requiring intensive treatment in an emergency room or at home, blood dyscrasias or convulsions that do not result in inpatient hospitalization, or the development of drug dependency or drug abuse.

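### Exclusion 22 both bars and permits a live vaccine shortly before Day 1, because its parenthesis is tied to an undefined enrollment date

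*Protocol*

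**What the plan says.** Section 4.2, under prior or current medications, item 22, has three parts in one sentence.

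- The first excludes a patient who "Received a live vaccine product within 14 days of study drug administration (Day 1" being the anchor in brackets.
- The second excludes a patient who expects a live vaccine during the Treatment Period.
- The third is a parenthesis: "receiving a live vaccine within 14 days prior to enrollment is allowed".

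The synopsis carries the same three parts, so comparing the two places reveals no correction.

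The timing text that bears on the reading is as follows.

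- Section 3.1 puts randomization and first dose on Day 1. Section 5.3.1 adds a tolerance: "Randomization (may occur on Day -1 if needed".
- Section 5.1 is headed "Screening Visit Procedures (Up to 2 weeks, Days -14 to -7", and consent is taken at that step. It adds that "screening may be extended up to one week to allow for retesting of lab test(s) that did not meet inclusion criteria".
- Section 3.4 gives screening as Days -14 to -1, at most two weeks, with no minimum.

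The protocol does not define enrollment. Section 4.1 item 4c says patients with raised beta-HCG "believed to be due to end-stage renal disease may be enrolled if documented to not be pregnant", a decision that can follow only after a pregnancy test, which is done at the Week -1 visit. Section 9.2 speaks of planned admissions "if the illness or disease existed before the patient was enrolled in the trial", in a sentence that also refers to signing the consent form. Both uses are general, and neither fixes a date.

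**The concern.** The parenthesis can only modify the 14-day restriction before Day 1. A vaccine given before enrollment is not one expected during the Treatment Period, which begins on Day 1, so the second part of the item gives it nothing to relax. Read naturally, it is an exception to the first part, and it permits what that part forbids.

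Most neighbouring time-limited exclusions use a usable anchor: randomization, the screening visit or the screening period. Item 22 uses Day 1 for the bar and an undated event for the permission.

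The criterion is protective. Section 3.7 says "Anti-inflammatory therapies in general run the risk of inducing immune suppression" and goes on to mention infections, some of them serious; Section 9.3 lists serious infections as events of special interest. Exposure is also slow to reverse: Section 3.5.4.1 gives mean terminal half-lives of 48 to 56 days in CKD patients. With approximately 50 to 60 sites interpreting the sentence, one could dose a patient whom another would screen-fail, and a monitor could not say which had deviated.

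**Working it through.** The plan states no figure here to reproduce. The check compares two date windows.

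**Inputs**

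- Barred window: the 14 days before Day 1 (Section 4.2, item 22). With no Day 0, these are Days -14 to -1, which matches Section 3.4 counting Days -14 to -1 as two weeks.
- Permitted window: the 14 days before enrollment (item 22, parenthesis).
- Candidate enrollment days: randomization on Day 1 (Section 3.1) or Day -1 (Section 5.3.1); consent on Days -14 to -7 (heading of Section 5.1); consent about Day -21 if the one-week retest extension is added to a full 14-day screening.

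**Formula**

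Let enrollment fall s days before Day 1. The permitted window then covers days s + 1 to s + 14 before Day 1, and the barred window covers days 1 to 14 before Day 1. Days in both = max(0, 14 - s).

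**Results**

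| Enrollment read as | s | Permitted window | Days both barred and permitted (of 14) |
|---|---|---|---|
| Randomization, Day 1 | 0 | Days -14 to -1 | 14 - 0 = 14 |
| Randomization, Day -1 | 1 | Days -15 to -2 | 14 - 1 = 13 |
| Consent, Day -7 | 7 | Days -21 to -8 | 14 - 7 = 7 |
| Consent, Day -10 | 10 | Days -24 to -11 | 14 - 10 = 4 |
| Consent, Day -12 | 12 | Days -26 to -13 | 14 - 12 = 2 |
| Consent, Day -14 | 14 | Days -28 to -15 | 14 - 14 = 0 |
| Consent, Day -21 | 21 | Days -35 to -22 | 0 |

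On the randomization reading the parenthesis cancels all or nearly all of the exclusion. On the consent reading the overlap is 0 to 7 days across the Section 5.1 window. That range depends on the heading: Section 3.4 sets no minimum screening length, and consent later than Day -7 would give more than 7 days.

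Where the overlap is zero, the permitted window lies wholly outside the barred one. The parenthesis then permits only what was never excluded and is redundant.

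**Example.** Consent on Day -7, live vaccine on Day -10, first dose on Day 1. The vaccine is 10 days before dosing, so the first part excludes the patient. It is 10 - 7 = 3 days before consent, so on the consent reading the parenthesis allows the patient.

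**Does any other text settle it?** Section 7.1 refers prior-medication restrictions back to Sections 4.1 and 4.2. Section 7.2 and Appendix A do not mention vaccines. Item 22 is the only live-vaccine rule in the protocol.

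**The case against.** The best defence is that the exclusion governs as it stands. Section 4.2 excludes anyone to whom any listed criterion applies, the first part of item 22 is plainly tied to Day 1, and exclusion 29 lets the investigator turn away any patient judged at increased risk. A cautious site would exclude the example patient. That is probably how many sites would act, but the text does not require it. The parenthesis is part of the criterion and reads as an exception to it, and nothing gives the first part priority.

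A second defence is that a compatible reading exists: if enrollment means entry to screening at Day -14 or earlier, the windows do not overlap. The arithmetic is right. However, the protocol does not say this, and on that reading the parenthesis serves no purpose.

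Three limits on the concern do stand.

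- Consent on Day -7 is the edge of the initial screening window. Screening is stepwise, with a separate Week -1 visit and a seven-day diary starting on Day -7, so the 7-day overlap is a boundary value and not a typical one.
- The uses of enrolled in Sections 4.1 and 9.2 are generic. They show that the term is undefined; they do not establish two distinct meanings.
- Section 3.7 speaks of immune suppression and infection in general. The protocol does not describe or quantify live-vaccine risk with this drug.

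**Conclusion.** The concern holds. Item 22 contradicts itself, almost completely if enrollment is randomization and partly if it is consent fewer than 14 days before Day 1. Defining enrollment as consent would not cure this by itself, because patients screened in under 14 days would still fall into both windows.

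The conclusion rests only on the two clauses of item 22 and the absence of a definition. The sizes rest on counting without a Day 0 and, for the consent range, on the Section 5.1 heading. The number of patients affected cannot be derived from the protocol. The point concerns eligibility and safety wording; it does not touch the sample size, power, type I error or intention-to-treat efficacy analysis. It should be corrected because sites act on this sentence directly and it is internally inconsistent as written.

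**What to change.** Delete the parenthesis from item 22 in Section 4.2 and in the synopsis, and use a single window anchored to first dose. Suggested wording:

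> Live vaccine received in the 14 days before the first dose of study drug (Day 1), or expected during the Treatment Period.

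If the clinical team meant the parenthesis to allow something specific, for instance a vaccine given more than 14 days before Day 1, that should be written out against the same Day 1 anchor.

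The cost is a one-sentence amendment in two places.

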### **General Exclusions**

28. Currently breastfeeding.

29. Any condition that could interfere with, or for which the treatment might interfere with, the conduct of the study or interpretation of the study results, or that would in the opinion of the investigator increase the risk of participating in the study.

#### **4.3 Criteria for Discontinuation of Study Drug**

It may be necessary for a participant to permanently discontinue study intervention. If study intervention is permanently discontinued, the participant shall remain in the study to be evaluated on all early termination and safety follow-up procedures per the Schedule of Assessments (SOA) in [Section 5.3.9](#) and [Section 5.6](#). Study drug may be prematurely discontinued for a number of reasons, including:

- An intercurrent illness at the discretion of the investigator;
- Any intolerable AE that cannot be ameliorated by appropriate medical intervention or that in the opinion of the Medical Monitor or Investigator would lead to undue risk if the patient were to continue on treatment;
- In the event of severe injection related reactions, anaphylaxis, or hypersensitivity ([Section 8.2](#) and [Section 4.5](#));
- If at any point during the study,  $\geq 10\%$  of subjects enrolled experience anaphylaxis, additional enrollment will stop in the study, and all patients in the study will discontinue receiving study drug ([Section 8.2](#) and [Section 4.4](#));
- Pregnancy;
- Organ transplantation or development of another indication for chronic immunosuppression;

Reasons for all withdrawals/discontinuations of Study Drug will be recorded, and the Medical Monitor should be informed of all such cases as they occur. Temporary discontinuation of study intervention and restarts may be performed per [Section 4.5](#).

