#### **4.6 Participant Discontinuation/Withdrawal from the Study**

The following are descriptions of participant discontinuation and withdrawal from the study. This is not an exhaustive list, and each instance should be evaluated on a case-by-case basis.

- Withdrawal of consent. A participant may elect to withdraw consent to treatment at any time.
- Participants withdrawing their consent for all study procedures must be given the option to continue to give consent for passive follow-up (i.e., by means of chart review) for AEs.
- Participants discontinuing study drug treatment after receiving any amount of study drug should undergo all early termination and safety follow-up study procedures per the SOA ([Section 5.3.9](#) and [Section 5.6](#)) unless the participant also explicitly withdraws consent for these procedures as mentioned above. The study drug has a long pharmacodynamic effect. Therefore, continued monitoring for pharmacodynamic effects and safety is prudent.

- A participant may be withdrawn at any time at the discretion of the investigator for safety, behavioral, compliance, or administrative reasons. Participation in the early termination and safety follow-up procedures will be evaluated on a case-by-case basis. If possible, participants should take part in the early termination and safety follow-up procedures in the SOA ([Section 5.3.9](#) and [Section 5.6](#)).
- If the participant withdraws consent for disclosure of future information, the sponsor may retain and continue to use any data collected before such a withdrawal of consent.
- If a participant withdraws from the study, the participant may request destruction of any samples taken and not tested. The investigator must document this in the site study records.

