**5.3.9                   Visit 10, Week 23 and Visit 11, Week 24/ET**

- Concomitant and Prior Medications
- Vital Signs
- BMI (Week 24 only)
- Hematology
- Lipids (fasting 8 hours)
- Chemistry
- Urinalysis (including albumin); portion stored frozen at Week 24 only
- Iron Indices
- Serum hepcidin (Week 24 only)
- Special RBCs (Week 24 only)
- IL-6
- hs-CRP
- Ziltivekimab trough PK
- ADA
- 12-lead ECG (Week 24 only)
- CKD Biomarkers
- NT-pro-BNP
- Lp(a), ApoB, ApoA1 (fasting 8 hours)
- Lipid profile by NMR spectroscopy (fasting 8 hours)
- Cardiac Biomarker: SSA, fibrinogen and ST2 (Week 24 only)
- Storage samples for Exploratory Biomarkers and RNA Testing (Week 24 only)
- Limited Physical Examination (Week 24 only)

- Coagulation (INR): Patients on warfarin only
- Adverse Events
- PROMIS® 13a and Fatigue Items
- PROMIS® Sexual Interest Items (Week 24 only)
- CARES (Corvidia ePRO) [2 weeks after Week 21 (Dose 6) for 14 consecutive days]
- PGIS (Week 24 only)
- PGIC (Week 24 only)
- Optum SF-36 v2®
- EQ-5D-5L (Week 24 only)

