## 5.6 Early Termination Visit

There are two possible types of Early Termination visits:

**Early Termination Visit 1 (ET-1):** Randomized patients terminating from the study prematurely prior to Study Week 24 should undergo an Early Termination Visit during which Week 24 procedures are performed.

**Early Termination Visit 2 (ET-2):** Randomized patients terminating from the study prematurely after Study Week 24 visit, but before Week 32 should undergo an early termination visit during which Week 32 procedures are performed.

Criteria for discontinuation of Study Drug can be found in [Section 4.3](#).

Patients may be withdrawn from the study for a number of reasons, including those outlined below:

- Patients withdrawing their consent for all study procedures. Patients must be given the option to continue to give consent for passive follow-up (i.e. by means of chart review) for adverse events through Study Week 21.
- Discontinuation of the study by the Sponsor.

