#### 11.3.2 Analysis Populations

**Intent-to-Treat (ITT) analysis population:** all patients randomized.

The ITT analysis populations will be the primary population for the analyses of disposition and baseline data and efficacy endpoints.

**Per-Protocol analysis population:** all patients randomized who completed the study and did not incur a significant protocol violation

For the ITT analysis populations and per-protocol populations, treatment classification will be based on the randomized treatment.

**Pharmacokinetics (PK) analysis population:** all patients randomized and who received at least one dose of Test or Reference product and who had at least one post-dose PK blood sample

**Safety analysis population:** all patients randomized and who received at least one dose of Test or Reference product.

For the PK analysis population and safety population, treatment classification will be based on the treatment actually received.

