### **11.3.3 Analysis Windows and Baseline**

If data are collected by visit, the data will be analyzed by visit based on the protocol-planned visits. If multiple records are collected for a visit, the latest record will be used for the summary for that visit.

The observational period for the study will start from informed consent and end with study completion (see [Section 4.4](#) for the definition of study completion). Any event occurring after the defined observational period, even if collected on the CRF, may not be included in the planned statistical analysis. However, all data, including that reported after the defined observational period, will be included in the patient data listings.

For evaluations that are collected at multiple occasions prior to initiation of Study Drug, the latest evaluation will be considered the "Baseline" evaluation for analysis, unless otherwise specified.

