#### 11.4.4.1 Primary

- Difference in percent change in hs-CRP levels from Baseline (average of the hs-CRP value prior to randomization and Day 1) to Week 13 between each active group and placebo.

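### Patients who permanently stop study drug are not required to attend Week 13, so the primary and secondary values are not secured for those who stop before it

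*Protocol*

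**What the plan says.** On permanent discontinuation, Section 4.3 says: "If study intervention is permanently discontinued, the participant shall remain in the study to be evaluated on all early termination and safety follow-up procedures". Section 4.6 says the same from the patient's side: "Participants discontinuing study drug treatment after receiving any amount of study drug should undergo all early termination and safety follow-up study procedures", unless consent for these procedures is withdrawn. Both cite Sections 5.3.9 and 5.6.

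- Section 5.3.9 is titled "Visit 10, Week 23 and Visit 11, Week 24/ET".
- Section 5.6 provides that randomized patients who terminate from the study before Week 24 "should undergo an Early Termination Visit during which Week 24 procedures are performed".
- The Week 13 assessments are in Section 5.3.7, which neither rule cites.

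On analysis, the primary endpoint (11.4.4.1) is the difference in percent change in hs-CRP from Baseline "to Week 13 between each active group and placebo". SAA and fibrinogen at Week 13 are the secondary endpoints (11.4.4.2). Section 11.3.2 states: "The ITT analysis populations will be the primary population for the analyses of disposition and baseline data and efficacy endpoints". The ITT population is everyone randomized. Sections 11.3.4 and 11.4.3 use observed data in an MMRM without imputation. Section 11.3.3 adds that, where data are collected by visit, "the data will be analyzed by visit based on the protocol-planned visits".

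**The concern.** An all-randomized analysis at Week 13 needs Week 13 measurements from randomized patients whether or not they are still on drug. The protocol names a different set of visits for those who stop, and it handles stopping drug and leaving the study through one path. A patient who stops after dose 1 or 2 and is willing to attend could therefore reach Week 13 with no instruction to take the sample.

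The reasons listed in 4.3 include intercurrent illness, intolerable adverse events and severe injection or hypersensitivity reactions. Several of these can plausibly move CRP, so the missing values may be informative. The MMRM would represent these patients by comparable patients who stayed under observation, most of them still on drug.

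Section 2 gives dose selection as the purpose of the trial. If stopping differs by dose, the comparison between doses could shift even when every dose clearly beats placebo.

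**Working it through.** **1. What is drawn, and when (visit lists, Sections 5.1 to 5.4)**

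- hs-CRP: initial screening, Day 1, Weeks 4, 5, 9, 13, 17, 21, 23, 24, 28 and 32.
- SAA (printed as SSA in the visit lists) and fibrinogen: Day 1, Week 13 and Week 24/ET only.

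A patient who stops before Week 13 may already have one or more on-treatment hs-CRP values from Weeks 4, 5 and 9, and these inform the MMRM. For SAA and fibrinogen there is no post-baseline value before Week 13; the early-termination sample would be the only one close to treatment. Patients who stop after the Week 13 visit already have all three values.

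**2. The plan's own sample size (Section 11.1)**

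Inputs: difference 60.74 points, SD 16.893, 54 evaluable per group, two-sided alpha 0.05, 10% dropout by end of study.

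- Standard error = 16.893 × √(2/54) = 3.25, and 60.74 / 3.25 = 18.7. Power is effectively 100%, so the statement of more than 99% is reproduced.
- 54 / 0.90 = 60 per group, also reproduced.
- With 48 per group the ratio is 60.74 / (16.893 × √(2/48)) = 17.6. With 30 it is 60.74 / (16.893 × √(2/30)) = 13.9. Power remains above 99% on the plan's effect and SD.

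Lost values are therefore a question of bias, not of power.

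**3. A ceiling for the bias**

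Let f be the share of an active arm that stops before Week 13 and is not measured then, Δ = 60.74 the on-drug difference, and ρ the share of the effect that remains in stoppers at Week 13. If all patients were measured, the difference would be Δ × (1 − f) + Δ × ρ × f. If stoppers are instead represented as though still on drug, the estimate is Δ. The overstatement is f × (1 − ρ) × Δ.

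The protocol does not give f, so these values are assumed:

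| f | patients of 60 | ρ = 0 (ceiling) | ρ = 0.5 (illustration) |
|---|---|---|---|
| 2.5% | 1.5 | 0.025 × 60.74 = 1.5 | 0.8 |
| 5% | 3 | 0.05 × 60.74 = 3.0 | 1.5 |
| 10% | 6 | 0.10 × 60.74 = 6.1 | 3.0 |

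At 10% with ρ = 0 the all-randomized difference would be −54.7 rather than −60.74. This is a ceiling for loss of drug effect; it assumes that stoppers on average do no worse than placebo.

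**4. Is ρ = 0 plausible?**

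Section 3.5.4.1 gives a half-life of 48 to 56 days in CKD patients, and dosing is every 28 days. With simple one-compartment accumulation, r = 0.5^(28/half-life) = 0.667 to 0.707. The Week 13 pre-dose level on schedule is proportional to r + r² + r³.

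- Dose 3 not given: (r² + r³) / (r + r² + r³) = 53% to 55% of the scheduled exposure.
- Doses 2 and 3 not given: r³ / (r + r² + r³) = 21% to 23%.
- Stopping between the Week 9 dose and Week 13: no dose before the Week 13 sample is missed, because that sample precedes dose 4.

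Exposure is not response, but drug remains on board in every dosed case.

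**5. Secondary matter: timing of an early-termination sample**

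By the same accumulation, (1 − r^k) / (1 − r^6), the trough 28 days after dose 1, 2 or 3 is about 33–36%, 57–61% or 74–77% of the dose-6 trough. An early-termination sample at about Week 6 would also lie 24 − 6 = 18 weeks from Week 24. If such a value were placed in the Week 24 slot, it would reflect clearly lower exposure.

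**The case against.** The routing is less absolute than it may look. Section 4.3 keeps the patient in the study, Section 4.6 calls further pharmacodynamic monitoring sensible, and Section 8.2 keeps patients with severe reactions under follow-up. Section 5.6 is triggered by leaving the study, not by stopping drug, and no sentence cancels scheduled visits. A reader might infer that no Week 13 sample will be taken from these patients. The text does not say so. It supports only that the sample is not required.

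A reader might also infer that early-termination values enter the model as Week 24. No sentence says this. It would follow only from the shared Week 24/ET label combined with analysis by planned visit, and the SAP, which is not at hand, may assign such records by study day. It would touch only the exploratory End of Treatment endpoints.

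The 1.5 to 6.1 point range should not be read as the expected bias. Its top places the whole 10% end-of-study dropout before Week 13 and assumes no remaining effect. That sits poorly with the half-life and with the hs-CRP decrease seen through eight weeks after a single dose (Section 1.4.2). Earlier hs-CRP values also enter the MMRM. Scope is limited further: temporary suspension (4.5) and missed doses (6.1.1) do not by themselves lead to early termination, and Section 11.4.3 commits to sensitivity analyses of the primary result.

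These limits stand. They do not remove the gap, because a sensitivity analysis must assume what an actual Week 13 sample would show, and SAA and fibrinogen have no earlier post-baseline value to lean on.

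**Conclusion.** The point holds as a gap in data collection. Following Sections 4.3 and 4.6 as written does not secure Week 13 hs-CRP, SAA or fibrinogen for patients who permanently stop drug before Week 13, while the analysis is of all randomized patients on observed data.

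The size is unknown, because the rate of stopping before Week 13 is not given. For hs-CRP the ceilings are 1.5, 3.0 or 6.1 points at assumed rates of 2.5%, 5% or 10%, and the true figure is likely smaller. On the plan's effect and SD, power stays above 99%, and nothing in the protocol suggests that the tests against placebo would reverse. What is exposed is the accuracy of the Week 13 estimates and of the comparison between doses, if stopping is related to CRP and differs by arm. That relation is plausible from the listed reasons but not shown by data in the protocol. This is an inexpensive improvement worth making prospectively, not a defect that invalidates the trial.

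**What to change.** - In Sections 4.3, 4.6 and 5.6, separate stopping study drug from leaving the study. State that patients who stop drug and still consent keep their scheduled assessments, at minimum Week 13 (hs-CRP, SAA, fibrinogen) and Week 24. Reserve the early-termination visit for those who leave the study.
- State in Section 11 that values obtained after stopping drug are used in the ITT analysis.
- As a secondary clarification, state in Section 11.3.3, or confirm in the SAP, that early-termination records are assigned by actual study day.

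The cost is amendment wording and a few already scheduled visits for the minority who stop drug but agree to attend. No new assay or procedure is needed, and the rules on when drug is stopped are untouched.
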